Global Use of Strategies to Open Occluded Coronary Arteries (GUSTO)

Major Bleeding endpoint will be defined by the GUSTO classification of “Severe” or “Moderate” as defined below:

Severe or life-threatening	Either intracranial hemorrhage or bleeding that causes hemodynamic compromise and requires intervention
Moderate	Bleeding that requires blood transfusion but does not result in hemodynamic compromise
Mild	Bleeding that does not meet criteria for either severe or moderate bleeding

Bleeding events that are medically important, but that do not meet the severe or moderate levels (e.g. require laboratory testing, evaluation by a physician, ER visit, or cessation of either study medication or other antithrombotic therapies) will be collected. Bleeding complications will be site reported.

CHRONIC CONCOMITANT MEDICATIONS

Chronic concomitant medication refers to the following:

- a) medication that has been prescribed or is over the counter, that has been taken or will continue to be taken regularly for at least a period of 3 months; or
- b) medication that is required to be taken indefinitely by the patient; or
- c) medication that has been prescribed or taken multiple times (each time for at least 3 months).

ENROLLED SUBJECT

Subject has signed the Informed Consent.

DWELL TIME

Start date and time the device was inserted into the sheath. Start date and time the device was deployed.

Family History of Coronary Artery Disease (CAD)

Family history of CAD is defined as CAD occurring in male 1st degree relatives (father, brothers) < 55 years old, and female 1st degree relatives (mother, sisters) < 65 years old.

INTENT TO TREAT [ITT] POPULATION

The ITT population is defined as the subjects registered in the study at the point of randomization.

LEGAL AUTHORIZED REPRESENTATIVE

An individual or judicial or other body authorized under applicable law to consent on behalf of a prospective subject to the subject's participation in the procedure(s) involved in the research. (21 CFR Part 50.3)

MAJOR EPICARDIAL VESSELS

- Left anterior descending artery [LAD] with septal and diagonal branches;
- Left circumflex artery [LCX] with obtuse marginal and/or ramus intermedius branches;
- Right coronary artery [RCA] and any of its branches.

NO-REFLOW

An acute reduction in coronary flow (TIMI grade 0-1) in the absence of dissection, thrombus, spasm, or high-grade residual stenosis at the original target lesion.

PERCUTANEOUS CORONARY INTERVENTION [PCI]

Refers to all interventional cardiology methods for treatment of coronary artery disease.

PRINCIPAL INVESTIGATOR

A physician-specialist, related to the study, who is responsible for the overall conduct of the trial at all sites and compliance with protocol and relevant.

PRIMARY INVESTIGATOR

A physician responsible for conducting the clinical trial at each investigational site.

PROCEDURE START DATE AND TIME

Procedure start date and time is recorded as the date and time the first guiding catheter was inserted into the subject.

PROCEDURE END DATE AND TIME

Procedure end date and time is recorded as the time the last guiding catheter was removed from the subject.

SUCCESSFUL PRE-DILATATION

Pre-dilatation has been successfully completed without complications if all of the following apply:

- For randomized subjects: RVD remains ≥ 2.50 mm - ≤ 3.75 mm and length of the lesion that will be covered by the device (including any edge dissections) is still ≤ 24 mm
- For Lead-In subjects: RVD remains ≥ 2.75 mm - ≤ 3.25 mm and length of the lesion that will be covered by the device (including any edge dissections) is still ≥ 8 mm - ≤ 14 mm
- Residual %DS is a maximum of $< 40\%$ (per visual estimation), $\leq 20\%$ is strongly recommended.
- TIMI Grade-3 flow (per visual estimation),
- No angiographic complications (e.g. distal embolization, side branch closure),
- No dissections NHLBI grade D-F
- No chest pain lasting > 5 minutes
- No ST depression or elevation lasting > 5 minutes.

TARGET LESION (Analysis Definition)

The target lesion is defined as the lesion that has met the angiographic inclusion and exclusion criteria in a registered subject upon calling IVRS.

Under these conditions, the lesion will be considered the target lesion regardless of the device implantation and treatment actually received.

TARGET VESSEL

The entire epicardial vessel in which the target lesion is located.

RANDOMIZED SUBJECT

Subject is considered randomized after the interactive voice response system (IVRS) has been called and a device (Absorb BVS or XIENCE) has been assigned.

REGISTERED SUBJECT

Subject is considered registered upon randomization. Lead-In subjects will be considered registered upon calling IVRS.

UNSTABLE CARDIAC ARRHYTHMIA

[figure not shown]
Any irregularity in the heart's natural rhythm associated with hemodynamic instability that has not been controlled in spite of treatment.

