APPENDIX II: DEFINITIONS

CLINICAL ENDPOINT DEFINITIONS

DEATH (Per ARC Circulation 2007; 115: 2344-2351)

All deaths are considered cardiac unless an unequivocal non-cardiac cause can be established. Specifically, any unexpected death even in patients with coexisting potentially fatal non-cardiac disease (e.g. cancer, infection) should be classified as cardiac.

Cardiac death (CD):

Any death due to proximate cardiac cause (e.g. MI, low-output failure, fatal arrhythmia), unwitnessed death and death of unknown cause, all procedure related deaths including those related to concomitant treatment.

Vascular death:

Death due to non-coronary vascular causes such as cerebrovascular disease, pulmonary embolism, ruptured aortic aneurysm, dissecting aneurysm, or other vascular cause.

Non-cardiovascular death:

Any death not covered by the above definitions such as death caused by infection, malignancy, sepsis, pulmonary causes, accident, suicide or trauma.

MYOCARDIAL INFARCTION (MI)

Protocol MI Definition

Classification	Biomarker Criteria	Additional Criteria
Periprocedural PCI	CK-MB > 5 x ULN	Baseline value* < ULN; see also **
Periprocedural CABG	CK-MB > 10 x ULN	Baseline value* < ULN; see also **
Spontaneous	Troponin >ULN or CK-MB > ULN	One or more of the following must also be present: - Symptoms of ischemia; - ECG changes indicative of new ischemia - (new ST-T changes or new LBBB), - Development of pathological Q waves; - Imaging evidence of a new loss of viable myocardium or a new regional wall motion abnormality
Reinfarction (not related to a procedure)	If the Troponin or CKMB values are stable or decreasing on 2 consecutive samples > 6 hours, a 20% or greater increase 3 to 12 hours after second sample is required to diagnose recurrent MI.	If biomarkers are increasing or peak not reached then insufficient data to diagnose recurrent MI. In this case at least two of the following three conditions must be present: - ECG changes indicative of new ischemia - (new ST-T changes or new LBBB), - Development of pathological Q waves - Imaging evidence of a new loss of viable myocardium or a new regional wall motion abnormality

ULN=Upper limits of the local laboratory normal (will be collected from each hospital laboratory prior to study commencement);

LBBB=Left Bundle-branch Block

* Baseline CKMB value is required before study procedure and presumes a typical rise and fall post procedure to diagnose a peri procedure MI

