- III. Marked limitation of ordinary activity; for example, angina occurs walking one or two blocks on the level or climbing one flight of stairs in normal conditions and at a normal pace.
- IV. Inability to carry on any physical activity without discomfort - angina syndrome may be present at rest.

CEREBROVASCULAR ACCIDENT/STROKE

Stroke is defined as a sudden onset of focal neurological deficits due to vascular lesions of the brain that persists >24 hours. Any neurological symptom that lasts < 24 hours is classified as TIA. Stroke results from either of two types of cerebral vascular disturbance: ischemia or hemorrhage.

DISCONTINUITY

Use when geometry of an implanted Absorb BVS has perceived or observed discontinuities (such as gaps, breaks or misalignment) on or after (\geq) 6 months post-procedure. Expected by design due to resorption process.

Fracture

When break is suspected to have occurred or reported during use or prior to (<) 6 months post-procedure (whichever is earliest)

DISSECTION

- **National Heart, Lung, and Blood Institute [NHLBI] Dissection Classification System:**
 - A. Minor radiolucencies within the lumen during contrast injection with no persistence after dye clearance.
 - B. Parallel tracts or double lumen separated by a radiolucent area during contrast injection with no persistence after dye clearance.
 - C. Extraluminal cap with persistence of contrast after dye clearance from the lumen.
 - D. Spiral luminal filling defects.
 - E. New persistent filling defects.
 - F. Non-A-E types that lead to impaired flow or total occlusion.

Note: Type E and F dissections may represent thrombus.

VASCULAR COMPLICATIONS (Am Heart J 2003; 145: 1022-9)

Access site injury requiring invasive treatment associated with protocol required procedures and unscheduled cardiac catheterizations. A vascular complication may include access site hematoma, pseudoaneurysm, arteriovenous fistula, peripheral ischemia or nerve injury.

OTHER PROTOCOL SPECIFIC DEFINITIONS

ANGINA

The first adverse event resulting in the site diagnosis of angina.

ASSIGNED DEVICE

In ABSORB III the assigned device for subjects in the Lead-In group is the investigational device Absorb BVS. For subjects in the randomized portion of ABSORB III (including the Imaging Cohort), the assigned device will be either the investigational Absorb BVS or the FDA approved XIENCE V, based on a 2:1 randomization.

BLEEDING CLASSIFICATION

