8.3 Adverse Event/ Device Deficiency/ Product Experience Reporting

8.3.1 Adverse Event and Serious Adverse Event Reporting

All adverse events will be collected on each subject through the 1-year follow-up visit. After one year, only the following will be collected:

- All serious adverse events.
- All cardiac events regardless of seriousness or device relationship.
- All trial device-related events and events for which the relationship to the trial device is unknown.
- All unanticipated adverse device effects.
- All Cerebral Vascular Accidents (CVAs).

The Investigator will monitor the occurrence of adverse events for each registered subject during the course of the clinical trial/investigation and report as required by this protocol in section 8 per AE and SAE definitions. Adverse Events reported by the subject, observed by the Investigator, or documented in medical records should be recorded on the adverse event eCRF, whether believed by the Investigator to be related or unrelated to the investigational device implant as required by this protocol.

A fax form will be made available to allow the investigator to report SAEs and device deficiencies in the event the entry cannot be made in the EDC (FRM2073001 SAE Notification Form). This does not replace the EDC reporting system, however, all information must still be entered in the EDC system as soon as feasible.

For all registered patients, AEs (any new event/experience that was not present at baseline or worsening of an event present at baseline) will be collected as required by this protocol. The reporting of AEs will start when the guiding catheter enters the subject's vasculature. Reported AEs will be monitored through the course of the trial. Additional information with regards to an AE should be updated within the appropriate case report form.

Unchanged, chronic, non-worsening or pre-existing conditions are not AEs and should not be recorded on the AE eCRF page.

The investigator should report all SAEs to the Sponsor as soon as possible but no later than outlined below.

Study site	Reporting timelines
------------	---------------------

All Study Sites	SAEs must be reported no later than 3 calendar days from the day the study personnel becoming aware of the event or as per the investigative site's local requirements if the requirement is more stringent than those outlined.
-----------------	--

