APPENDIX II: DEFINITIONS

Please refer to **Appendix II** of ABSORB III Protocol ([REDACTED], March 14, 2017) for complete list of definitions. New or updated definitions are listed below:

MYOCARDIAL INFARCTION (MI)

Protocol MI Definition: Periprocedural MI definition is modified from Moussa ID, Klein LW, Shah B, Mehran R, Mack MJ, Brilakis ES, Reilly JP, Zoghbi G, Holper E, Stone GW. Consideration of a new definition of clinically relevant myocardial infarction after coronary revascularization: an expert consensus document from the Society for Cardiovascular Angiography and Interventions (SCAI). J Am Coll Cardiol. 2013 Oct 22;62(17):1563-70.

This definition will be used for the primary analysis of ABSORB IV and secondary analysis of ABSORB III.

Classification	Biomarker Criteria	Additional Criteria
Periprocedural – patients with a) stable CAD, or b) silent ischemia, or c) acute coronary syndromes with at least 2 baseline troponin values which remained <ULN, or d) acute coronary syndromes in whom the troponin and/or CK-MB levels were elevated but all returned to <ULN prior to the procedure	Absolute CK-MB rises within 48 hours of the procedure to > 5 x ULN for post-PCI or CK-MB > 10 x ULN for post-CABG	Baseline value* < ULN; see also **
Periprocedural – patients with stable CAD and elevated baseline CK-MB, or acute coronary syndromes in whom at least 2 baseline troponin and CK-MB values were drawn and the most recent troponin and CK-MB values were less than the preceding measures by >25%	Absolute incremental CK-MB rise within 48 hours of the procedure from the most recent CK-MB level by > 5 x ULN for post-PCI or > 10 x ULN for post-CABG	

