2.1.2 Statistics for Categorical Variables

For categorical variables such as gender, MACE, and TVF, results within treatment arm will be summarized with subject counts and percentages/rates, and where specified in the table mockups, with exact 95% Clopper-Pearson³ confidence intervals. Differences between the two treatment arms, when specified, will be summarized with the difference in percents and the Newcombe⁴ score 95% confidence interval for the difference of two percentages.

For efficacy and safety endpoint(s), relative risks (i.e., the ratio of rates), confidence interval for the relative risks, the difference in rates and the confidence interval for difference in rates (using previously-described formulas), and p-values may also be presented for hypothesis generating purposes. The p-values will be based on either Pearson's Chi-square test or Fisher's exact test by checking the expected frequency for each cell in the 2x2 contingency table against Cochran's rule⁶, i.e., if the expected frequencies for all cells are ≥ 5 , then Pearson's Chi-square test will be used, otherwise Fisher's exact test will be used.

For the determination of event rates at all time points (in-hospital, 30 days, 180 days and 1 to 7 (8/9/10) years), the denominators are defined as below based on the type of events.

- Death/MI/Revascularization (DMR) event

Subjects will be included in the analysis if they either had the DMR event by that time or they did not have the DMR event but had follow-up through that time point. In other words, subjects will be included in a given analysis if it can be determined whether or not the subject would have had the DMR event by the time point.

- Stent/Scaffold Thrombosis, Vascular/Bleeding, CVA, and Angina

Subjects will be included in the analysis if they either had the specific event (for example, for analysis on ST, only ST is considered) by that time or they did not have the event but had follow-up through that time point. In other words, subjects will be included in a given analysis if it can be determined whether or not the subject would have had the event by the time point.

Formulas for calculating confidence intervals for the categorical variables are given below.

1. 100(1- α) % Exact Clopper-Pearson Confidence Interval for A Single Proportion³

$$\text{Lower Confidence Limit} = \frac{x}{x + (n - x + 1)F_{1-\frac{\alpha}{2}}(2(n - x + 1), 2x)}$$

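### The stroke definition makes no exception for death, so a stroke fatal within 24 hours drops out of the CVA tabulation, though not out of the death, SAE or bleeding records

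*Protocol*

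**What the plan says.** The entry on cerebrovascular accident and stroke in ABSORB III Appendix II opens: "Stroke is defined as a sudden onset of focal neurological deficits due to vascular lesions of the brain that persists >24 hours". The next sentence reads: "Any neurological symptom that lasts < 24 hours is classified as TIA". A third sentence names ischemia and hemorrhage as the two mechanisms of stroke. The entry has no alternative criterion based on death, imaging or autopsy, and neither document has another readable definition of stroke.

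ABSORB IV Appendix II refers back to the ABSORB III appendix "for complete list of definitions. New or updated definitions are listed below". Stroke is not among the entries that follow, so the same wording governs ABSORB IV.

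The stroke category is used in two places:

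- SAP section 2.1.2 sets denominators for event rates at all time points and has a group headed "Stent/Scaffold Thrombosis, Vascular/Bleeding, CVA, and Angina". Its rule begins: "Subjects will be included in the analysis if they either had the specific event (for example, for analysis on ST, only ST is considered". The alternative route into the analysis is to be free of that event and followed to the time point.
- Section 8.3.1 of both trials lists what is still collected after year 1, including "All Cerebral Vascular Accidents (CVAs". TIA is not on that list.

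**The concern.** A duration criterion separates stroke from TIA among patients who survive long enough to be observed. It fails for a patient who dies first. The deficit never resolves, yet it cannot meet the 24-hour requirement. The strokes that fail the definition are therefore the rapidly fatal ones.

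Subjects in both trials take aspirin and a P2Y12 inhibitor for at least 12 months, and ABSORB III section 16.2 warns of sometimes fatal bleeding with two of the permitted agents. An early fatal intracranial bleed is thus a foreseeable event. A CVA row by arm that omits it understates the count, and counts this low can look different after one event is moved.

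**Working it through.** The plan states no figure that depends on this definition, so the check is textual, followed by a bound on the size.

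**Step 1. Classify one case.** Take a stroke fatal 10 hours after onset.

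| Classification | Criterion | Result |
|---|---|---|
| Stroke/CVA (Appendix II) | Deficit lasting more than 24 hours | Not met |
| TIA (Appendix II) | Any neurological symptom under 24 hours | Met on the literal wording |
| Death by cause (Appendix II) | "Death due to non-coronary vascular causes such as cerebrovascular disease, pulmonary embolism" | Vascular death; cardiac death if procedure-related or of unknown cause |
| SAE (section 8.1.2) | Led to death | Met |
| Bleeding (GUSTO, Appendix II) | "Either intracranial hemorrhage or bleeding that causes hemodynamic compromise and requires intervention" | Severe, if haemorrhagic |

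Only the CVA line loses the event. A procedure-related fatal stroke, being a cardiac death, also enters TLF.

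Other entries in the same appendix do provide for early death. The universal MI definition covers death before biomarkers could be obtained, and probable stent thrombosis covers unexplained death in the first 30 days. The stroke entry has no such provision. A deficit of exactly 24 hours also falls in neither class, because both limits are strict.

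**Step 2. Apply the SAP rule.** The subject has no qualifying CVA and, after death, no follow-up to later time points. Neither route into the analysis set is open. With x true CVAs among n evaluable subjects, the reported rate is (x − 1)/(n − 1) instead of x/n. The difference is (n − x)/[n(n − 1)], close to 1/n when x is small. For n = 1,300, 1/1,300 = 0.077%, or about 0.08 percentage points per early fatal stroke.

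**Step 3. Bound the number of events.**

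- Arm size: 2,600/2 = 1,300 (ABSORB IV, 1:1).
- Frequency: stroke, CVA and TIA together are listed as uncommon, 0.1% to below 1.0%, at 1 year (ABSORB III Appendix VIII; ABSORB IV Appendix VI).
- Combined events per arm: 1,300 × 0.001 = 1.3 to 1,300 × 0.01 = 13. This includes TIAs, so it is a ceiling for strokes and not a stroke count.
- Share fatal within 24 hours: not in the documents. I assume 2% to 15%.
- Events affected per arm: 1.3 × 0.02 = 0.03 to 13 × 0.15 = 1.95.

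The plausible loss is therefore 0 to 2 events per arm at 1 year. At 2 events the rate moves by about 2/1,300 = 0.15 percentage points.

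**The case against.** The strongest reply is that little depends on this. CVA is not a named endpoint in section 5 of either trial or in the readable part of SAP section 1.3.2.3, and its only readable SAP role is in the denominator rule. The death, the SAE and any intracranial haemorrhage are recorded whatever the CVA label. The definition applies equally to both arms. All of this stands, and it is why the point is minor.

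A second reply is that no adjudicator would call a fatal haemorrhage a TIA, since Appendix I expands the term as a transient ischemic attack and the stroke entry itself recognises hemorrhage. That is a fair answer to anyone who infers that such deaths would be tabulated as TIAs. It does not make the event a stroke, because the 24-hour requirement in the first sentence is still unmet.

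A third reply is that the adjudication text may deal with the case. ABSORB III section 9.1 is not readable here, so such a rule cannot be excluded, but no readable text supplies one.

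A reader might also infer that the appendix contradicts itself, because one patient can be a cerebrovascular death and a severe bleed but not a CVA. These are separate classifications with separate criteria. The result is awkward, but the vascular-death entry does not depend on the stroke criterion.

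**Conclusion.** The point holds in a limited form. As written, a stroke fatal within 24 hours is not a CVA, and the SAP rule then removes that subject from the CVA rate altogether. TLF at 30 days and 1 year, angina, the margins and the power are unaffected. Severity is minor.

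Two stronger readings should be resisted. The first is that the most severe strokes, including fatal bleeding on dual antiplatelet therapy, vanish from the safety record. They leave one descriptive row and remain under deaths, SAEs and, if haemorrhagic, severe bleeding. The second is that the CVA rate is understated by some definite percentage. Any such figure only restates an assumed early-fatal share, and the documents give neither that share nor a frequency for stroke alone.

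The estimate of 0 to 2 events per arm rests on the combined 0.1% to below 1.0% range and the assumed 2% to 15%. The conclusion also assumes that the CVA tabulation uses the Appendix II definition, since the SAP rule cites none, and that no unseen adjudication rule overrides it. Finally, the ABSORB IV cross-reference dates the ABSORB III appendix March 14, 2017, while other cross-references give August 16, 2018. I take the stroke entry to be the same in both.

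**What to change.** Reword the stroke entry in ABSORB III Appendix II to: *focal neurological deficit of vascular origin persisting 24 hours or more, or leading to death earlier*. Limit TIA to: *transient focal deficit of presumed vascular origin that resolves in less than 24 hours*. This also settles the case of exactly 24 hours and stops a brief non-vascular symptom from qualifying as a TIA. State that the revised entry applies to ABSORB IV, and have SAP section 2.1.2 cite it for the CVA rate. If the events committee already has a rule for early fatal strokes, write that rule into Appendix II.

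The cost is a short wording change. No new data are needed, because deaths and SAEs are already collected; deaths already recorded as cerebrovascular would need a check against the new wording. The only downside is a possibly slightly higher reported CVA rate.
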